13.4.2 LEO Pharma reporting responsibilities

Global Safety at LEO Pharma is responsible for assessing whether or not an SAE is expected. The relevant reference safety information documents for this clinical trial are:

- For the IMP, the investigator's brochure section 7.2, edition 19 and subsequent updates must be used.
- For AxMP (mometasone furoate, 0.1% cream), the latest version of the summary of product characteristics (SmPC) must be used.

Pharmacovigilance at LEO Pharma K.K. will notify the regulatory authorities and concerned investigators of SAEs according to the current applicable legislation for the concerned country.

The IRBs/IECs will be notified of SAEs according to the current applicable legislation for the concerned country.

All SAEs which are assessed as causally related to the IMP(s) by **either the investigator or LEO Pharma (33)**, and which are unexpected (Suspected, Unexpected Serious Adverse Reactions [SUSARs]), are subject to expedited reporting to regulatory authorities, IECs/IRBs according to the current applicable legislation for the concerned country. Investigators will be notified of the evolving safety profile of the IMP on an ongoing basis.

13.5 Other events that require expedited reporting

13.5.1 Pregnancy

Any pregnancy occurring after first exposure to IMP and until the subject has completed the trial must be reported to LEO Pharma K.K. within 24 hours of first knowledge using the (paper) pregnancy form (part I). All pregnancies must be followed up until delivery or

termination and final outcome must be reported on the (paper) pregnancy form (part II) within 24 hours of first knowledge.

The completed pregnancy forms must be faxed or scanned and e-mailed to Pharmacovigilance at LEO Pharma K.K. Contact details are given in Section [13.4.1](#).

Pregnant subjects must immediately discontinue IMP permanently (Sections [10.2.1](#) and [10.3](#)).

13.6 Reporting of other events

13.6.1 Adverse events of special interest

The events listed in [Panel 10](#) are considered AEs of special interest (AESIs) in this trial and will require additional details to be recorded in the eCRF. LEO Pharma may request that the investigator forward test results, as appropriate. An AESI may be serious (requiring expedited reporting, Section [13.4](#)) or non-serious.

Panel 10: Adverse events of special interest

AESI	Additional data to be recorded in the eCRF (if available ¹)
Eczema herpeticum	
Skin findings:
 
 • Lesion type (papules, vesicles, crusts, eroded pits, other). • Disseminated/localised. • Location (face, scalp, back, chest, upper limb, lower limb, genitals). • Present in an area with visible eczema / no visible eczema / present in areas with and without eczema. • Monomorphic/polymorphic. • Confirmation of herpes simplex virus (not confirmed, PCR, viral culture, Tzanck, other).
Malignancy diagnosed after randomisation, excluding basal cell carcinoma, localised squamous cell carcinoma of the skin, and carcinoma in situ of the cervix	
 • Histology report available. • Oncology assessment available. • Treatments (surgery, radiation, chemotherapy, other).
Skin infection requiring systemic treatment	
 • Location (face, scalp, back, chest, upper limb, lower limb, genitals). • Outcome of pathogenic swab (positive, negative, not performed).
Conjunctivitis	
 • Aetiology (viral, bacterial, allergic, unknown). • Bacterial culture outcome (for events with bacterial aetiology). • Diagnosis confirmed by ophthalmologist.
Keratoconjunctivitis	
 • Aetiology (infectious, non-infectious, other, unknown). • Bacterial culture outcome (for events with bacterial aetiology). • Diagnosis confirmed by ophthalmologist.
Keratitis	
 • Aetiology (infectious, non-infectious, other, unknown). • Bacterial culture outcome (for events with bacterial aetiology). • Diagnosis of herpes simplex keratitis (for events with viral aetiology). • Diagnosis confirmed by ophthalmologist.

1) The additional data to be recorded in the eCRF are not a requirement, but are to be reported by the investigator, if available, for example as part of standard clinical practice.

Abbreviations: AESI, adverse event of special interest; eCRF, electronic case report form; PCR, polymerase chain reaction.

13.6.2 Overdose

An overdose is defined as a subject receiving a quantity of IMP which is in excess of that specified in this protocol. An overdose is either accidental or intentional.

The term 'overdose' including a specification of why it occurred (accidental or intentional) must be recorded on the AE form of the eCRF. In addition, AEs originating from overdose

must be recorded as separate events. If the AE originating from the overdose qualifies as an SAE, expedited reporting is required (Section 13.4).

If the overdose is accidental and due to a device deficiency, the device deficiency must be reported as a product complaint as described in Section 9.10.

LEO Pharma does not recommend specific treatment for an overdose. The investigator will use clinical judgement to treat any overdose if necessary.

13.6.3 Medication error

Medication error refers to any unintentional error in the dispensing or administration of an IMP while in the control of the investigator or subject. Broadly, medication errors fall into 3 categories: wrong medication, wrong dose (including strength, form, concentration, amount), wrong route of administration.

The medication error category must be documented on the AE form in the eCRF. In addition, AEs originating from a medication error must be recorded as separate events. If the AE originating from the medication error qualifies as an SAE, expedited reporting is required (Section 13.4).

If the medication error is due to a device deficiency, the device deficiency must be reported as a product complaint as described in Section 9.10.

13.6.4 Misuse

Misuse refers to situations where the IMP is intentionally and inappropriately used not in accordance with the protocol.

The term ‘misuse’ must be recorded on the AE form in the eCRF. In addition, AEs originating from misuse must be recorded as separate events. If the AE originating from misuse qualifies as an SAE, expedited reporting is required (Section 13.4).

13.6.5 Abuse

Abuse relates to the sporadic or persistent, intentional excessive use of an IMP which is accompanied by harmful physical or psychological effects.

The term ‘abuse’ must be recorded on the AE form in the eCRF. In addition, AEs originating from abuse must be recorded as separate events. If the AE originating from abuse qualifies as an SAE, expedited reporting is required (Section 13.4).

13.6.6 Aggravation of condition

Any clinically significant aggravation/exacerbation/worsening of any medical condition(s), compared to screening, must be reported as an (S)AE in accordance with Sections [13.3](#) and [13.4](#). As AD is a fluctuating disease, consider to only report an AE if the aggravation/exacerbation exceeds normal disease fluctuation or if lesions appear in a body area which is normally not affected by AD.

13.7 Follow-up for final outcome of adverse events

During the trial, the investigator should follow up for final outcome on all AEs (including SAEs). Once a subject leaves the clinical trial, the investigator should follow up on the outcome of all non-serious AEs classified as of possibly or probably related to the IMP for 2 weeks or until the final outcome is determined, whichever comes first. SAEs must be followed up until a final outcome has been established, that is, the follow-up may continue beyond the end of the clinical trial. For SAEs which have stabilised and from which the subject cannot be expected to recover during the trial or the safety follow-up periods, for example chronic or stabilised conditions, the final outcome at the investigator's discretion should be reported as 'recovering/resolving' or 'not recovered/not resolved'. In addition, a statement detailing why the subject cannot be expected to recover during the trial e.g. that the SAE has stabilised or is chronic should be added to the narrative description of the SAE on the SAE form.

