Main objectives and endpoints	
Primary objective
 
To evaluate the efficacy of tralokinumab in combination with topical corticosteroids (TCS) compared with placebo in combination with TCS in treating moderate-to-severe atopic dermatitis (AD).
 
Secondary objective (efficacy)
 
To evaluate the efficacy of tralokinumab in combination with TCS on severity and extent of AD, itch, health-related quality of life (HRQoL), and health care resource utilisation compared with placebo in combination with TCS.
	
Primary endpoints
 
 Investigator's Global Assessment (IGA) score of 0 (clear) or 1 (almost clear) (IGA 0/1) at Week 16. At least 75% reduction in Eczema Area and Severity Index (EASI75) at Week 16. 
Key secondary endpoints
 
 Change in Scoring Atopic Dermatitis (SCORAD) total score from baseline to Week 16. Change in Dermatology Life Quality Index (DLQI) score from baseline to Week 16. Reduction of Worst Daily Pruritus numeric rating scale (NRS) score (weekly average) ≥ 4 from baseline to Week 16. 
Secondary endpoints
 
 At least 90% reduction in Eczema Area and Severity Index (EASI90) at Week 16. At least 50% reduction in Eczema Area and Severity Index (EASI50) at Week 16. Percentage change in Eczema Area and Severity Index (EASI) score from baseline to Week 16. Change in Worst Daily Pruritus NRS score (weekly average) from baseline to Week 16. Change in Eczema-related Sleep NRS score (weekly average) from baseline to Week 16. Change in Patient-Oriented Eczema Measure (POEM) score from baseline to Week 16.

		
Other endpoints
 
 Reduction of DLQI score ≥ 4 points from baseline to Week 16 in subjects with baseline DLQI score ≥ 4. Reduction of POEM score ≥ 4 points from baseline to Week 16 in subjects with baseline POEM score ≥ 4. Amount of TCS (auxiliary medicinal product [AxMP]) used at Week 16. TCS (AxMP) use < 5g at Week 16. Cumulative amount of TCS (AxMP) used from baseline to Week 16.
	
Secondary objective (safety)
 
To assess the safety of tralokinumab in combination with TCS when used to treat moderate-to-severe AD for 16 weeks.
	
Secondary endpoints
 
 Number of treatment-emergent adverse events (AEs) from baseline to Week 16 per subject. Presence of treatment-emergent anti-drug antibodies (ADA) from baseline to Week 16.

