9.2 Administration of trial products

9.2.1 Administration of IMP

IMP administration visits are shown in the schedule of trial procedures (Section [4](#)). The IRT will assign the required IMP kit number for each subject at each IMP administration visit.

The first day of IMP administration is considered Day 0 (Week 0; Visit 3), where each subject will receive 4 SC injections (each 1.0 mL) of 150 mg tralokinumab or placebo to receive a total loading dose of 600 mg tralokinumab or placebo.

At subsequent visits in the treatment period, each subject will receive 2 SC injections (each 1.0 mL) of 150 mg tralokinumab or placebo every 2 weeks to receive a total dose of 300 mg tralokinumab Q2W or placebo Q2W. The last IMP administration will occur at Week 14.

The IMP will be administered by a qualified, unblinded healthcare professional (HCP); see Section [9.3.1](#) for blinding details. A minimum interval of 7 days is required between 2 administration visits.

The injections will be administered into the SC tissue of the upper arm, anterior thigh, or abdomen, separated by at least 3 cm. The injection site must be recorded in the source documents and in the eCRF at each IMP administration visit (Section [9.8.4](#)).

Further details on IMP administration are provided in a trial product handling manual. The IMP administration must be carried out according to these instructions.

LEO Pharma does not have any specific treatment recommendations in relation to overdose. The investigator will use clinical judgement to treat any overdose, if necessary. See Section [13.6.2](#) for further details regarding overdose.

Monitoring after IMP administration

For the first 3 IMP administration visits (i.e. Weeks 0, 2, and 4), each subject will be monitored after the IMP administration for immediate drug reactions for a minimum of 30 minutes with vital signs taken at 30 minutes or until stable, whichever is later. Vital signs will be documented in the eCRF (Section [11.4.1](#)).

As with any antibody, allergic reactions to dose administration are possible. The World Allergy Organization has categorised anaphylaxis into 2 subgroups: allergic anaphylaxis

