9.2.2 Administration of AxMP (TCS)

The IRT will assign the required AxMP (TCS) kit number for each subject at each AxMP dispensing visit. The AxMP dispensing visits are shown in the schedule of trial procedures (Section [4](#)). The subject must return used and unused AxMP (TCS tubes) at each subsequent trial visit to assess the amount of TCS used. The subjects must be instructed by the site staff on the importance of returning all used and unused TCS tubes. The site staff will return used and unused TCS tubes to the contract manufacturing organisation (CMO). The returned TCS tubes will be weighed at the CMO.

Each subject will be instructed to apply a thin film of the dispensed AxMP (TCS) once daily on active lesions of AD, as needed. The TCS should be discontinued when control is achieved; discontinuation should preferably be gradual, and the maximum duration of a treatment course should not exceed 3 weeks. The safety and appropriateness of continued or repeated courses of TCS therapy will be monitored and supervised by site staff.

The AxMP (TCS) should be the only TCS product applied to the body during this period. Lower potency TCS or TCI may be used at the investigator's discretion on areas of the body where use of the supplied AxMP (TCS) is not advisable such as areas of thin skin (face, skin fold areas, genital areas, etc.) or on areas where continued treatment is considered unsafe. The low potency TCS and TCI will not be provided by LEO Pharma and will not be weighed but must be registered in the eCRF as concomitant medications (Section 9.6).

The supplied AxMP (TCS) is only for use on active lesions of AD and not for use in other indications.

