13.3 Reporting of adverse events

AEs reported by the subject or observed by the investigator must be recorded on the AE form of the eCRF and should be described in the following manner:

The *AE term* must be in precise English medical terminology (that is, not necessarily the exact words used by the subject). Whenever possible, a specific diagnosis should be stated (for example ‘allergic contact dermatitis’).

The *duration* of the AE must be reported by the start date and stop date of the event (if the event is ongoing it will also be recorded). In addition, it must be recorded whether the AE started on the same day as the IMP administration (i.e. before or after dosing).

AEs must be classified in terms of severity, causality, and outcome according to the definitions in [Appendix 2](#). For events not considered related to IMP, the causal relationship to the use of AxMP should be evaluated using the same definitions as for the IMP.

Action taken with trial treatment: any action taken with IMP or AxMP as a consequence of the AE must be recorded (dose not changed, dose reduced, dose increased, drug interrupted, drug withdrawn, not applicable, unknown).

Other action taken: any other action taken as a result of the AE must be recorded (none, concomitant medication, concurrent procedure).

Withdrawn from trial due to this AE: it must be recorded whether the AE led to withdrawal from the trial.

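### Section 13.7 follows non-serious AEs after exit only if IMP-related, so an open AE attributed to TCS never qualifies, although the safety objective is the combination

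*Protocol*

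**What the plan says.** - **After exit, non-serious events (Protocol 13.7).** The duty is to "follow up on the outcome of all non-serious AEs classified as of possibly or probably related to the IMP for 2 weeks"; it ends sooner if the outcome is known. Only the IMP is named, and the IMP is tralokinumab or placebo (7.1, 9.1.1). The mometasone cream is a separate auxiliary product, the AxMP (9.1.2).
- **During the trial, and serious events (13.7).** All AEs are followed for outcome during the trial, whatever their cause. SAEs are followed until a final outcome, beyond the end of the trial if necessary.
- **Order of causality rating (13.3, repeated in Appendix 2).** "For events not considered related to IMP, the causal relationship to the use of AxMP should be evaluated". The AxMP rating is a second step, reached only after the IMP has been ruled out.
- **Safety objective (synopsis).** "To assess the safety of tralokinumab in combination with TCS when used to treat moderate-to-severe AD for 16 weeks".
- **Where AxMP is covered.** Action taken with AxMP is recorded (13.3), the SAE report assesses AxMP causality (13.4.1), and AxMP-related AEs are tabulated by arm (14.3.12.1).
- **SAP.** Section 6.7.1 assigns AEs to periods and summarises them. It does not change the follow-up rule.

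**The concern.** The protocol treats TCS as part of the regimen whose safety is being assessed, and asks for a TCS causality rating on any event not ascribed to the IMP. The sentence on follow-up after exit then ignores that rating. A subject may leave with an unresolved non-serious reaction that the investigator puts down to the supplied cream. The protocol sets no duty to find out how that reaction ended, whereas a comparable reaction put down to the injection would be followed.

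At stake is the final outcome of such events, for the individual subject and for the outcome data on the combination. No reason for the different treatment is given.

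**Working it through.** No arithmetic underlies the rule, so the check is to set the conditions side by side.

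**Step 1: can a TCS-attributed non-serious AE meet the 13.7 condition?**

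- Condition for an AxMP rating (13.3, Appendix 2): the event is judged not related to the IMP.
- Condition for follow-up after exit (13.7): the event is judged possibly or probably related to the IMP.
- Appendix 2 offers three IMP ratings: probably, possibly and not related. The first condition takes the third category and the second takes the other two. No event satisfies both.

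| Event and attribution | During the trial | After exit |
|---|---|---|
| Non-serious, IMP possibly or probably | followed | 2 weeks, or to outcome if sooner |
| Non-serious, not IMP, TCS possibly or probably | followed | no rule |
| Non-serious, neither product | followed | no rule |
| Serious, any attribution | followed | to final outcome |

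The second row is the gap. The third row is an ordinary limit on follow-up and is not criticised.

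**Step 2: who leaves with such an event open?**

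- *Completes treatment and attends Week 20.* The all-AE rule runs through safety follow-up, which lasts 20 − 16 = 4 weeks after the treatment period in which TCS is supplied. That exceeds the 2 weeks in 13.7, so little is lost.
- *Enters the extension trial at Week 16.* These subjects have no safety follow-up visit (7.1), so they leave with 16 − 16 = 0 weeks of in-trial follow-up after the treatment period. Under 13.2, an ongoing AE is also recorded as medical history in the extension. The extension protocol is not among the documents, so whether outcomes are pursued there cannot be judged.
- *Withdraws early.* Section 10.3 provides an early termination visit and refers AE follow-up back to 13.7, so the same IMP condition applies.

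**Step 3: does another section repair it?** No. Sections 13.2, 13.3, 13.4.1, 14.3.12.1 and Appendices 1 and 2 concern collection, rating, serious events or tabulation. None extends follow-up after exit to AxMP-related non-serious events.

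**Step 4: does an endpoint depend on it?** No. The safety endpoints are the number of treatment-emergent AEs per subject and the presence of treatment-emergent ADA, both to Week 16. Neither uses an outcome recorded after exit.

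**The case against.** The strongest reply is that little is lost and that the IMP-only scope is a defensible choice. TCS is auxiliary treatment given in both arms, with the product's own SmPC as reference safety information (13.4.2). Appendix 2 lets an event be possibly related to the IMP even when other therapies could explain it, so many events with a mixed explanation would be rated IMP-related and followed. Events open at exit still receive a recorded status (recovering, not recovered or unknown). All of this stands, and it limits the size of the point. It does not explain why an event rated as caused by one component of the combination is followed and an event rated as caused by the other is not.

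A reader might infer two stronger things that the documents do not support.

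- *That TCS-attributed AEs are left out of the safety data.* They are not. They are collected, rated, followed during the trial, followed to outcome if serious, and tabulated.
- *That overdose, medication error, misuse and abuse (13.6.2 to 13.6.5) should be rewritten to cover TCS.* Those definitions do name only the IMP. Overdose, for example, reads "An overdose is defined as a subject receiving a quantity of IMP which is in excess of that specified in this protocol". But 9.2.2 sets no maximum TCS quantity. Its limit is one of time ("the maximum duration of a treatment course should not exceed 3 weeks"), so an AxMP overdose would have nothing to be measured against. These terms also go on the AE form. A harm-free departure from 9.2.2 could then enter the treatment-emergent AE count, unevenly if TCS use differs by arm. Nor is TCS use untracked: tubes are weighed (9.8.3.2), topical use is entered daily in the eDiary (11.3.4.3), site staff supervise repeated courses (9.2.2), and any resulting harm is an AE under Appendix 1.

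**Conclusion.** The point holds in a narrow form. By construction, every non-serious AE formally attributed to TCS and unresolved at exit falls outside the follow-up rule in 13.7. In practice this concerns mainly early withdrawals and subjects who move to the extension at Week 16.

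The number of such events cannot be derived, because the documents give neither a rate of TCS-related AEs nor the expected share of subjects entering the extension. The amount of cream supplied would not help, since use is as needed and supply says nothing about harm.

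The conclusion assumes that sites apply 13.3 and 13.7 as written. An investigator who follows such events anyway, as good practice, would close the gap without being asked to. Sample size, efficacy analyses and safety endpoints are unaffected. This is a cheap improvement to safety follow-up and does not threaten the trial's validity.

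**What to change.** In 13.7, replace 'related to the IMP' with 'related to the IMP or AxMP' and keep the existing follow-up period. This brings 13.7 into line with 13.3, 13.4.1 and 14.3.12.1. The AxMP causality rating it needs is already required by 13.3, so no new assessment is added. The cost is a wording change and a few extra follow-up contacts.

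Leave 13.6.2 to 13.6.5 as they are. At most, the sponsor could add a sentence saying whether those four terms are meant to exclude AxMP. No change to the TCS regimen is involved.

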13.8 Handling of an urgent safety measure

An urgent safety measure is a measure taken to implement an action/protocol deviation under an emergency. This is defined as "*...the occurrence of any new event relating to the conduct of the trial or the development of the investigational medicinal product where that new event is likely to affect the safety of the subjects, the sponsor and the investigator shall take appropriate urgent safety measures to protect the subjects against any immediate hazard.*" ([34](#)).

If the investigator becomes aware of information that requires an immediate change in a clinical trial procedure or a temporary halt of the clinical trial to protect clinical trial subjects from any immediate hazard to their health and safety, the investigator can do so without prior approval from LEO Pharma, regulatory authorities, or IRBs/IECs.

The investigator must immediately inform LEO Pharma – by contacting the clinical project manager or medical expert – of this change in a clinical trial procedure or of the temporary

halt; the investigator will provide full details of the information and the decision-making process leading to the implementation of the urgent safety measure.

LEO Pharma must act immediately upon receipt of the urgent safety measure notification in accordance with internal procedures and local legislation.

14 Statistical methods

